#### *At least one eye, designated as the “study eye,” must meet all the following inclusion criteria:*

9. Study eye displays GA lesion(s) measuring a total area between approximately 1.5 sqmm and 20 sqmm (between ~0.5 and ~9 Disc Areas), measured on fundus autofluorescence imaging (FAF), as confirmed by sponsor.
10. Study eye presents hyperautofluorescent patterns in the junctional zone of GA.
11. If GA lesions are multifocal in the study eye, one lesion at least must be approximately 1.00 sqmm or greater.
12. In case of foveal sparing in the study eye, the smallest distance between GA border and foveal center must be less than approximately 250 µm.
13. All GA lesions in the study eye must fit entirely within the 30-degree retinal imaging field centered on the fovea.
14. Study eye has BCVA of 33 letters (~20/200) or better.
15. Study eye has clear or adequate ocular media and pupillary dilation, including no allergy to dilating eyedrops, to permit good quality retinal imaging.

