1.0. INTRODUCTION

This Statistical Analysis Plan (SAP) describes the statistical methodology and data handling for the study ALK001-P3001, A Phase 2/3 Multicenter, Randomized, Double-masked, Parallel-group, Placebo-controlled Study to Investigate the Safety, Pharmacokinetics, Tolerability, and Efficacy of ALK-001 in Geographic Atrophy (GA) Secondary to Age-related Macular Degeneration (AMD). This SAP is based on protocol ALK001-P3001 version 1.1, dated 01Feb2019. This SAP was prepared prior to database lock and unmasking. Any deviations from this SAP will be documented in the Clinical Study Report (CSR).

The trial consists of a treatment period of 24 months and is designed to obtain evidence on the effects of gildeuretinol acetate, also named “ALK-001” in this plan, on the mean rate of growth (slope) estimated based on GA area and measured on fundus autofluorescence (FAF) imaging.

The following guidelines were used as a guide to write this plan:

- ICH E3 structure and content of clinical study reports
- ICH E9 statistical principles for clinical trials
- ICH E9 (R1) addendum on estimands and sensitivity analysis in clinical trials to the guideline on statistical principles for clinical trials

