3.1. Overall Study Design

This is a randomized, double-masked, parallel-group, multicenter study evaluating the safety and efficacy of ALK-001 in subjects with GA secondary to AMD.

Approximately 300 subjects were planned to be randomized in a 2:1 ratio to receive either ALK-001 at 14 mg/day or placebo daily for a total treatment duration of 24 months. There was no stratification for randomization, and subjects were randomized using random permuted blocks of size 3 and 6. Due to enrollment delays caused by COVID-19, 200 subjects were randomized with the same 2:1 randomization. Subjects, investigators and study staff, and sponsor staff who may be in contact with investigators or subjects, are masked until after this SAP is submitted to FDA and database lock has occurred.

After an initial screening day (V01), subjects are given a placebo to take once a day during a run-in period. The placebo is indistinguishable from ALK-001, and subjects are unaware that they are receiving the placebo. The run-in period typically lasts between 2 and 4 weeks. At the conclusion of the screening and run-in period, subjects who meet all eligibility criteria were randomized on Day 1 (V02).

Following randomization at V02, subjects have follow-up visits scheduled at Month 6 (V04), Month 12 (V06), Month 18 (V08), and Month 24 (V10) after starting treatment on Day 1. Treatment discontinues at Month 24 (V10). A diagram of the study design and timelines is provided below.

The follow-up visits encompass various assessments. Safety and tolerability will be assessed by monitoring AEs, clinical laboratory tests (biochemistry, hematology, lipids), vital signs, ECG, physical examinations, and pharmacokinetics. Efficacy assessments include GA area measured on FAF imaging, BCVA, LLVA, reading speed, VFQ-25, FRI, microperimetry (optionally performed at sites where available), etc. (Refer to [Appendix 1](#) for a full list of assessments and visit schedule).

Each subject's study duration is up to 2 years and 4 weeks, including screening and run-in period and the 2-year treatment. The study will end when the last subject completes Visit V10 (Month 24) or discontinues the study.

Following completion of the initial treatment period of 2 years, subjects may be given the choice to enter a two-year open-label extension study, which is not covered in this SAP.

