3.2. Sample Size

The initial sample size was based on literature data on the progression of GA at the time the study was started. With 300 subjects and assuming that 80% of subjects are evaluable for the primary outcome measure, the study has an 80% power to detect, after 24 months of treatment, a 33% slowing in GA growth rate with a 2-tailed significance of 0.05, assuming a conservative standard deviation of 1.5 mm²/year and an average GA growth rate of 1.8 mm²/year in the control group.

Based upon natural history literature data updated as of the date of this SAP, and the area of GA, indicating an average GA growth rate of 1.8 mm²/year with a standard deviation of 1.2 mm²/year, with 200 subjects and considering that 80% of subjects completed the study and are expected to

have evaluable data for the primary outcome measure, the study has an 80% power to detect, after 24 months of treatment, a 33% slowing in GA growth rate with a 2-tailed significance of 0.05.

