6.1. Analyses of Primary Efficacy Endpoint

An Eligible Eye is defined as an eye with (a) measurable GA and (b) no presence of CNV at baseline as determined centrally by a central reading center according to combined review of optical coherence tomography (OCT) and color fundus photograph (CFP) (“Multimodal imaging”), and FA. GA lesion size will be measured independently by three readers on FAF imaging. The final GA lesion size (area) for each subject’s Eligible Eye, adjudicated from the assessments by three readers, will be used in the analysis.

The primary efficacy endpoint is the mean rate of growth (slope) in the GA area as measured by FAF from baseline to Month 24.

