6.1.3 Main Analysis of Primary Efficacy Endpoint

The mean rates of change (slope) in the GA area will be computed for the ALK-001 and the placebo arms, by use of a linear mixed-effects model applied to the GA area measured on FAF images at time points (baseline, Month 6, Month 12, Month 18 and Month 24) assuming time as continuous and linear (“slope model”).

The analysis model will use the change from baseline in the GA area measured by FAF as the response variable, and will include treatment arm (ALK-001, placebo), pattern of FAF at the junctional zone of GA (banded/diffuse, focal/other/cannot grade), GA lesion multifocality (multifocal, unifocal/other/cannot grade) and foveal status (foveal sparing, subfoveal/cannot grade) as fixed effects, baseline GA lesion area and time (year, continuous assuming linearity) as

covariates, time \times treatment interaction, and baseline GA lesion area \times time interaction. Random effects include subject and subject's eye (OD or OS). A common unstructured covariance matrix will be used to model the within-subject errors, and the Kenward-Roger's (Kenward and Roger 1997) method will be used to estimate denominator degrees of freedom. If the model fails to converge, alternative structures (heterogenous autoregressive (1), heterogeneous compound symmetry, autoregressive (1), or compound symmetry, in this order) will be considered.

The mean rate of change (mm^2/year), standard error, and 95% confidence interval (CI) will be estimated from baseline to Month 24 for each treatment arm. The estimated difference in slopes among the treatment groups along with the 95% CIs and p-value will be provided to test the significance of the treatment effect.

The observed values for the GA area (mm^2) of Eligible Eyes will be summarized by treatment group and visit. Summaries will present the descriptive statistics for baseline, absolute values and change from baseline data.

The mean change from baseline \pm the standard error in the GA area (mm^2) of Eligible Eyes as well as the Least-Squares (LS) mean of the change from baseline \pm the standard error in GA area (mm^2) of Eligible Eyes will be plotted over time by treatment group.

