6.1.6 Subgroup Analyses of Primary Efficacy Endpoint

Subgroup analyses will be performed to evaluate the consistency of the primary analysis results across subgroups defined by demographic and baseline characteristics. The main analysis described in [Section 6.1.3](#) will be repeated for the primary efficacy endpoint for each of the following subgroups:

- **Age group:** <75 years, ≥75 years at enrollment
- **Sex:** male, female
- **Baseline BCVA:** BCVA 64 letters (~20/50) or better, BCVA less than 64 letters
- **Baseline LLD:** LLD 30 letters or more, LLD less than 30 letters
- **Baseline GA lesion size:** small (< 7.5 mm²), large (≥ 7.5 mm²)
- **Baseline GA lesion multifocality:** multifocal, unifocal
- **Baseline GA lesion foveal status:** foveal sparing, subfoveal

Forest plot will be produced for mean rate of change (mm²/year) or slope of total GA area (mm²) from the baseline to Month 24 for each treatment arm, difference in mean rate of change and associated 95% CI for overall population and by subgroups.

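### Three baseline lesion factors enter the primary slope model without time interactions, so they barely touch the growth-rate comparison; adding those interactions is a cheap improvement with a small possible loss

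*SAP*

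**What the plan says.** SAP section 6.1.3 takes change from baseline in GA area as the response, treats time as continuous and linear, and tests the difference in slopes. FAF junctional pattern is listed as a fixed effect, along with "GA lesion multifocality (multifocal, unifocal/other/cannot grade) and foveal status (foveal sparing, subfoveal/cannot grade) as fixed effects, baseline GA lesion area and time". The interactions are time by treatment and baseline area by time ("treatment interaction, and baseline GA lesion area" is where that list runs). FAF pattern, multifocality and foveal status have none.

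Nothing later fills this in. The piecewise analysis (6.1.4) and the sensitivity analyses (6.1.5) repeat the same covariate structure or change the response, the time scale or the analysis set. Section 6.1.6 states that "Subgroup analyses will be performed to evaluate the consistency of the primary analysis results across subgroups defined by demographic and baseline characteristics"; multifocality and foveal status are subgroup factors there, and FAF pattern is not.

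Three further points bear on this. On allocation, section 3.1 says "There was no stratification for randomization". The analysis unit can be either or both eyes of a subject: "An Eligible Eye is defined as an eye with (a) measurable GA and (b) no presence of CNV at baseline" (section 6.1). The introduction says "This SAP was prepared prior to database lock and unmasking".

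**The concern.** The response is zero at time zero by construction, so a baseline feature that predicts growth must act through the slope. The SAP follows this logic for baseline area and, without giving a reason, not for the other three. A reader would assume the growth-rate comparison is adjusted for all four.

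What is lost is precision, and correction for any chance imbalance in these factors, which unstratified randomization does not prevent. The subgroup analyses are no substitute: they give no adjusted overall contrast and leave out FAF pattern.

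**Working it through.** **1. Why the main effects do not help.** Take one eye per subject and complete visits. Each subject's data reduce to an intercept and a slope. The slope equation contains treatment and baseline area; the intercept equation contains those plus the three factors. When one equation's regressors are a subset of the other's, its generalized least squares estimate ignores the extra regressors. The slope difference is therefore identical with or without the three factors.

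**2. With dropout or two eyes.** The identity is then only approximate, so it was simulated: 100 runs per setting; visits at 0.5, 1, 1.5 and 2 years; baseline area by time in the model; three factors explaining 10% or 20% of slope variance. Assumptions not in the documents: measurement-error SD 0.35 mm², between-eye correlation 0.6. Largest change in the slope difference from adding the three main effects:

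| Data | Largest change (mm²/year) |
|---|---|
| One eye, complete | 2e-15 |
| Half of subjects with two eyes, complete | 0.005 |
| One eye, 20% dropout | 0.021 |
| Two eyes and dropout | 0.025 |

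The model standard error (SE) moved by at most 0.0001.

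**3. The plan's own power.** SAP section 3.2 works "with 200 subjects and considering that 80% of subjects completed the study": 0.80 × 200 = 160 evaluable. At 2:1 that is 106.7 against 53.3. The SD is 1.2 mm²/year and the difference is 0.33 × 1.8 = 0.594 mm²/year.

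SE = 1.2 × √(1/106.7 + 1/53.3) = 0.2012. A two-sided t-test at 0.05 (noncentral t, 158 df) gives 83.5%, against the stated 80%. The stated figure is on the cautious side, and the main effects do not alter it.

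**4. With the three time interactions.** Let R² be the share of slope variance the three factors explain beyond baseline area by time. Then SE = 1.2 × √[(1 − R²)(1/106.7 + 1/53.3)(160 − 3)/(160 − 6)], with 155 df. The ratio 157/154 charges for three extra parameters. Equivalent N is 160 × (0.2012/SE)². The documents give no R², so a range is shown.

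| R² | SE | Power | Equivalent evaluable N |
|---|---|---|---|
| 0% | 0.2032 | 82.8% | 157 |
| 2% | 0.2012 | 83.5% | 160 |
| 5% | 0.1981 | 84.6% | 165 |
| 10% | 0.1928 | 86.5% | 174 |
| 20% | 0.1817 | 90.1% | 196 |
| 30% | 0.1700 | 93.5% | 224 |

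Break-even is at about R² = 2%.

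**5. Simulated check of the gain and the test level.** In 1,000 simulated trials per setting (200 subjects, one eye, about 20% dropout, estimated unstructured covariance, assumed measurement-error SD 0.3 mm²), moving from the SAP model to the model with interactions changed power from 88.4% to 87.3% at R² = 0, from 87.6% to 91.4% at 10%, and from 86.9% to 93.4% at 20%. The levels exceed the formula because dropouts contribute their earlier visits. Type I error was 4.3% with the interactions and 4.3–4.8% for the SAP model.

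**6. Chance imbalance.** For a 50/50 feature explaining R², the two levels differ in slope by 2 × 1.2 × √R². A 10-point imbalance between arms shifts the estimate by a tenth of that: 0.05, 0.08 or 0.11 mm²/year at 5%, 10% or 20%, that is 0.27, 0.38 or 0.53 SE. The confidence interval already allows for this; adjustment would remove most of it.

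**The case against.** The strongest reply is that nothing is broken: the test is valid, the stated power is met, and imbalance of this kind is ordinary sampling error. That is correct and sets the weight of the point.

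The size, and even the sign, of the benefit depends on an R² that the documents do not give. Eligibility also narrows the spread of two factors in study eyes: Protocol section 1.8.1 requires that "Study eye presents hyperautofluorescent patterns in the junctional zone of GA", and limits how far GA may lie from the foveal center when the fovea is spared. Small R² values are therefore plausible, and the 20–30% rows have no support in the documents.

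The table may also run high, because it uses the raw SD although baseline area by time already absorbs some variance. If that term explains 10%, 20% or 30% (assumed), reference power is about 87%, 90.5% or 94%, and the gain at R² = 10% falls from 3.0 points to about 2.6, 2.2 or 1.6. With two eyes per subject and complete data, simulation at R² = 10% gave an SD falling from 0.1985 to 0.1926, about 2 points of power by the normal formula.

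These objections shrink the gain. None of them makes the main effects useful for the slope contrast.

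**Conclusion.** The concern holds as an optional efficiency improvement. As written, FAF pattern, multifocality and foveal status contribute essentially nothing to the treatment-by-time comparison: exactly nothing with one eye and complete data, and at most about 0.025 mm²/year in any simulated trial otherwise.

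Giving them time interactions costs about 0.7 power points by formula (1.1 in simulation) if they do not predict growth. It gains about 1 point at 5% explained slope variance, 3 at 10% and almost 7 at 20%, somewhat less with two eyes per subject or if baseline area is itself a strong predictor. These figures rest on the SAP's SD, effect and evaluable share, and on an assumed R². Neither the estimand nor the validity of the planned test is in question.

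**What to change.** Before unmasking, add FAF pattern by time, multifocality by time and foveal status by time to the section 6.1.3 model, and state that arm-specific slopes are reported at the observed covariate margins. The treatment-by-time coefficient remains the slope difference.

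Carry the terms into the analyses that repeat the model: piecewise, multiple imputation, per protocol, square root and the other repeats in 6.1.5.3. The piecewise model needs one term per factor and segment, so six. The categorical-time analyses need factor-by-visit terms. In the multifocality and foveal-status subgroups, drop the term for the factor that defines the subgroup.

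If the SAP can no longer be changed, leave the primary test alone, add this model to 6.1.5.3 as a labelled sensitivity analysis, and say plainly that the three covariates do not adjust the slope comparison.

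The cost is SAP wording, re-programming and three extra slope parameters in the primary model, with no new data. Arm-specific slopes would depend on the stated margins, and the loss from extra parameters is larger in small subgroups than in the full set.

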6.1.4 Piecewise Analysis

The mean rate of change in the GA area will be compared between the ALK-001 arm and the Placebo arm by use of a piecewise linear mixed-effects model assuming time as continuous and piecewise linear ("piecewise slope model").

The analysis to be performed will be similar to what is described in [Section 6.1.3](#) except that a breakpoint (knot) at Month 12 visit will be added which allows for the slope of lesion growth to differ between the period of baseline to Month 12 and the period of Month 12 to Month 24 for each treatment group. The mean rate of change (mm^2/year) for baseline to Month 12 and for Month 12 to Month 24, their associated standard error, and 95% CI will be estimated for each treatment arm. The estimated difference in slopes for baseline to Month 12 and for Month 12 to Month 24 among the treatment groups along with the 95% CIs and p-value will be provided.

Similarly, a breakpoint (knot) at Month 6 will be added, and similar outputs for Month 6 to Month 24 will be provided.

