2.2.3 Secondary Efficacy Endpoints

- Growth rate of the total area of GA lesion(s) between baseline and Month 12
- Growth rate of the total area of GA lesion(s) between Month 12 and Month 24
- Growth rate of the total area of GA lesion(s) between Month 6 and Month 24

- Change from baseline in LLD score
- Change from baseline in maximum reading speed at Month 24, as measured by MNRead (wpm)
- Change from baseline in binocular reading speed, as measured by IReST
- Change from baseline in FRI Index score at Month 24
- Change from baseline in VFQ-25 total score
- Incidence of CNV in the study eye, when the fellow eye has CNV at baseline

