4.7. Derived Variables and Parameters

Variables requiring calculation will be derived using the following formulas:

- Duration of study (month) = (last study participation date – informed consent date +1)/ 30.4375
- Duration of exposure (day) = last treatment date – reference start date +1
- Duration of exposure (month) = duration of exposure (day)/30.4375
- Percentage of duration of exposure (%) is calculated as [total number of days with no lapse in treatment (day)]/ [duration of exposure (day)] x 100.
- Change from baseline = postbaseline value – baseline value
- Percentage change from baseline = ([postbaseline value – baseline value] / baseline value) x 100
- Low Luminance Deficit (LLD) = one eye's Best Corrected Visual Acuity (BCVA) score – Low Luminance Visual Acuity (LLVA) score

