6.1.5.3. Other Sensitivity Analyses

The main analysis described in [Section 6.1.3](#) will be repeated with the following modifications:

- **Square root of the GA lesion area:** using the change from baseline in the square root of the GA lesion area instead of the change from baseline in the GA lesion area as response variable and replacing baseline GA lesion area by square root of baseline GA lesion area in the model.
- **Restriction on baseline area:** subject eyes are included only if GA lesion at baseline exceeds 0.5 mm².
- **Only first 12 months:** excluding all data points after the 12-month visit.
- **Absolute change at Month 24:** using change from baseline in GA lesion area as response variable, assuming time as categorical, for both the GA area and the square root of GA area. Replacing baseline GA lesion area by square root of baseline GA lesion area in the model for analysis of the square root of GA area.

The LS mean of the change from baseline in GA area (mm²) of Eligible Eyes \pm the standard error will be plotted over time by treatment group, assuming time as categorical.

- **Percentage change at Month 24:** using percentage change from baseline in GA lesion area as response variable, assuming time as categorical, for both the GA area and the square root of GA area. Replacing baseline GA lesion area by square root of baseline GA lesion area in the model for analysis of the square root of GA area.
- **Exclusion of eyes with CNV at baseline or historical determined by PI:** Eligible Eye(s) reported to have CNV at baseline or in medical history will be excluded from the analysis.

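### The piecewise growth-rate analyses are fitted to change from baseline without saying whether baseline is a response row; on the usual reading the Month 6 to 24 rate repeats the primary slope and the baseline to Month 12 rate is a Month 6 to 12 rate

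*SAP*

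**What the plan says.** SAP section 6.1.3 defines the slope model. On the response it says: "The analysis model will use the change from baseline in the GA area measured by FAF as the response variable". The fixed part gives each arm its own level as well as its own slope: "and will include treatment arm (ALK-001, placebo), pattern of FAF at the junctional zone of GA" is followed by time, time by treatment, and baseline area by time. On covariance: "A common unstructured covariance matrix will be used to model the within-subject errors". If the fit fails to converge, the fallbacks are, in order, heterogeneous AR(1), heterogeneous compound symmetry, AR(1) and compound symmetry.

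Two statements bear on which rows enter. Section 6.1.3 says the model is applied to GA area "at time points (baseline, Month 6, Month 12, Month 18 and Month 24", so baseline is listed. Section 4.7 begins its definition with "Change from baseline = postbaseline value" and subtracts the baseline value, so a change is defined only after baseline.

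Section 6.1.4 keeps this model, puts a knot at Month 12 and reports a rate on each side of it. It continues: "Similarly, a breakpoint (knot) at Month 6 will be added, and similar outputs for Month 6 to Month 24 will be provided". Section 2.2.3 lists three interval rates as secondary endpoints: baseline to Month 12, Month 12 to 24, and "Growth rate of the total area of GA lesion(s) between Month 6 and Month 24". A sensitivity analysis in section 6.1.5.3 refits the main model "excluding all data points after the 12-month visit".

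**The concern.** The interval rates can show whether an effect on lesion growth appears early or late. A slope model can do this only if it has information on both sides of each knot and at the start of the first segment. With change from baseline as the response, the natural starting point (zero change at time zero) is either left out of the data or enters as a constant with no variance. If it is left out, the arm intercepts absorb whatever happened before Month 6, which is the first scheduled follow-up visit (section 3.1). The Month 6 knot then adds nothing, and a rate labelled as starting at baseline in fact starts at Month 6. Because the SAP does not state the rows, two programmers could follow it and report different values for the same endpoint.

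**Working it through.** No figure in the SAP depends on this, so there is nothing to reproduce. The check concerns what the model can estimate.

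**Inputs.** Placebo growth is 1.8 mm²/year and the slowing is 33% (section 3.2), so the rate difference is 0.33 × 1.8 = 0.594 mm²/year. Follow-up visits are at 0.5, 1, 1.5 and 2 years. One eye per subject is assumed. The time-constant factors (FAF pattern, multifocality, foveal status) are left out because they do not change the result.

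**Reading A: post-baseline rows only, nominal time.**

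*Month 6 knot.* The columns are intercept, arm, baseline area, time, arm × time, baseline area × time, knot and arm × knot: 8 in all. The knot term is max(t − 0.5, 0). At every visit t ≥ 0.5, so:
- knot = time − 0.5 × intercept
- arm × knot = arm × time − 0.5 × arm

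Both are exact combinations of existing columns, so the rank is 6 of 8. If baseline area is also interacted with the knot it is 6 of 9. The slope after Month 6 remains estimable and equals the primary slope. A GLS fit to simulated data with 160 subjects at 2:1 gave -0.0371 for both under a random-slope covariance and under compound symmetry, and -0.0432 for both under AR(1).

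*Month 12 knot.* The rank is full, 8 of 8. The first segment, however, is identified by Month 6 and the fitted value at Month 12. Let D(t) be the arm difference in mean change at t years. The true baseline to Month 12 rate difference is D(1)/1. When the pattern from Month 6 is linear, as in all three cases below, the model returns (D(1) − D(0.5))/0.5.

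| Timing of the 33% slowing | D(0.5) | D(1) | True rate, baseline to Month 12 | Model's first segment |
|---|---|---|---|---|
| Months 0–6 only | -0.297 | -0.297 | -0.297 | 0/0.5 = 0.000 |
| From Month 6 only | 0 | -0.297 | -0.297 | -0.297/0.5 = -0.594 |
| Throughout (linear) | -0.297 | -0.594 | -0.594 | -0.297/0.5 = -0.594 |

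The 12-month sensitivity analysis has only the Month 6 and Month 12 rows and the same free arm intercept. Its slope difference is therefore the last column again.

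*Precision when the effect is linear.* This needs variances that the SAP does not give. Assume a slope SD of 1.15 (just under the SAP's 1.2), a measurement SD of 0.2 to 0.4 mm², and 107:53 evaluable subjects, so 1/107 + 1/53 = 0.02821.
- Two-visit Month 6–12 rate: variance 1.15² + 8 × SD², giving SE √(1.6425 × 0.02821) = 0.215 to √(2.6025 × 0.02821) = 0.271.
- Month 12 change: variance 1.15² + 2 × SD², giving SE √(1.4025 × 0.02821) = 0.199 to √(1.6425 × 0.02821) = 0.215.

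The full fit borrows slightly from later visits (0.214 rather than 0.215 at the lower end).

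**Reading B: zero-change baseline rows included.** The Month 6 knot design has full rank. With the effect confined to Months 0–6 and compound symmetry, the primary slope difference is the least-squares slope of D = (0, -0.297, -0.297, -0.297, -0.297) on t = (0, 0.5, 1, 1.5, 2). That is -0.297/2.5 = -0.119. The Month 6 to 24 difference is 0.000, and baseline to Month 12 is about -0.289 against -0.297. The endpoints are then separate and close to what their names say.

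Change at baseline, however, is zero for every eye. The baseline row and column of the covariance are all zeros and the determinant is 0, so the specified unstructured matrix is degenerate. Heterogeneous AR(1) and heterogeneous compound symmetry also give baseline its own variance, which is again zero. Only AR(1) and compound symmetry can be fitted, and they give baseline the same variance as Month 24.

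**The case against.** The best case for the plan has four parts.

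First, section 6.1.3 names baseline among the model's time points, and the last two fallback structures can be fitted with baseline rows. This stands, and it rules out saying without condition that the Month 6 to 24 endpoint is the primary slope printed twice. It does not settle the matter. Section 6.2.2 uses the same list of time points for an MMRM of change in LLVA, section 4.7 points the other way, and the baseline reading works only after three covariance structures have failed.

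Second, exact aliasing needs nominal times. The SAP calls time continuous in years without saying nominal or actual. The events table in protocol version 1.1 allows visits up to a week early, and SAP section 4.4 maps early-termination data from Day 91 to Month 6. With actual dates some observations fall before the knot. This also stands: the equality is then approximate, and the segment before Month 6 rests mainly on a few days of spread.

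Third, the 0.000 and -0.594 results come from extreme timing scenarios. That is correct. Under a linear effect, which the primary model assumes, the estimates are unbiased. Departures from linearity are nevertheless what interval rates are meant to reveal.

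Fourth, early-versus-late information is already planned through the by-visit summaries in 6.1.3 and the categorical-time model in 6.1.5.3. That limits the harm, but it does not make the named endpoints estimate their intervals.

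**Conclusion.** The point holds conditionally and is of moderate weight. As written, neither way of running sections 6.1.3 and 6.1.4 delivers the interval endpoints cleanly. With post-baseline rows and nominal time, the Month 6 to 24 rate duplicates the primary slope, and the baseline to Month 12 rate and the 12-month sensitivity slope are Month 6 to 12 rates. Those two can be wrong by 0.297 mm²/year in either direction if a 33% slowing is confined to one side of Month 6. With zero-change baseline rows the intervals are estimable, but only under the last two fallback covariances. The rank and bias results follow from the model's structure and the SAP's 1.8 mm²/year and 33%; the standard errors rest on assumed variances.

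Three stronger inferences are not supported. A reader might say that the Month 6 to 24 endpoint estimates the wrong interval; on the post-baseline reading it estimates its own interval and is only redundant. A reader might extend the aliasing to the Month 12 to 24 rate, which it does not affect. A reader might conclude that the primary test or the error rate is compromised. The hierarchy in section 6.2.1 covers only the primary endpoint, LLVA and BCVA, and the slope difference is correct when there is no effect or a linear one. The choice of rows does decide which months the primary slope rests on, so it should be stated for that model too.

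**What to change.** State in section 6.1.3 which visits are response rows and whether time is nominal or actual. Then replace the knot models as the source of the three secondary rates with LS-mean contrasts between arms from the categorical-time model of change in GA area already in section 6.1.5.3:
- baseline to Month 12: Month 12 change ÷ 1 year
- Month 12 to 24: (Month 24 − Month 12) ÷ 1 year
- Month 6 to 24: (Month 24 − Month 6) ÷ 1.5 years

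Use the Month 12 contrast for the 12-month sensitivity analysis as well.

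Alternatively, keep the knots but fit them to GA area itself with baseline as a response row. The baseline-area covariate terms would then need revising, since baseline would be part of the outcome.

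The cost is SAP wording and a few contrast statements, with no new data. Little precision is lost for Month 6 to 24. With slope SD 1.15 and measurement SD 0.2, the contrast SE is √((1.3225 + 2 × 0.04/2.25) × 0.02821) = 0.196, within about 0.001 of the slope's. If unmasking has already occurred, report the contrasts as a documented deviation in the study report, as SAP section 1.0 provides.
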